3.8.2 Secondary Efficacy Endpoints

The secondary efficacy endpoints, fasting plasma glucose, sitting systolic and diastolic blood pressure and weight, will be analyzed using the same MMRM ANCOVA model used for the primary efficacy analysis on the full analysis set. In addition, for each secondary efficacy endpoint, the least squares means and standard errors of the change from baseline over time by treatment group will be presented graphically. Sensitivity analyses will not be performed on the secondary efficacy endpoints.

For each subject, post-baseline HbA1c values will be reviewed and subjects with at least one post-baseline HbA1c value $<7\%$ will be flagged. HbA1c values obtained after start of rescue medication will be excluded from this analysis. The number and percentage of subjects with at least one HbA1c value $<7\%$ will be summarized by treatment group for the full analysis set. A logistic model will be used to characterize treatment differences in the proportions of subjects with at least one post-baseline HbA1c value $<7\%$. For this model, the dependent variable will take values of $1 = '<7\%'$ or $0 = '≥7\%'$ and the predictor variables will include treatment, study center, baseline HbA1c and prior anti-diabetic treatment status. Odds ratio for the treatment difference versus placebo, its 95% confidence interval and the associated p-value will be presented.

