3.4 Study Duration and Dates

Diabetic subjects will be screened within 3 weeks of enrollment. Eligible subjects who provide written consent will start a 2 to 12 week washout and run-in period prior to randomization to receive investigational product. Subjects will receive 12 weeks of treatment and be followed for 2 weeks after the last dose. The study duration from screening to follow-up will be 16 weeks and up to 29 weeks overall (Figure 3). For details of the schedule and nature of the investigations, see the Schedule of Events in [Appendix 1](#).

[figure not shown]

Figure 3. THR-1442-C-449 Study Design

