7.4 Exit Visit or Early Termination Visit

7.4.1 Visit V5 (week 14 or two weeks after the last dose of investigational product if a subject early terminates)

At the V5 visit the study investigator will:

- Review SMBG and glycemic control record
- Perform a complete physical examination including weight
- Measure vital signs, including blood pressures, pulse, temperature, and respiratory rate
- Perform a 12-lead ECG measurement
- Draw blood from subjects who have fasted a minimum of 10 h as described in [Section 6.7.2.1](#). The specific laboratory tests scheduled for this visit are listed in [Appendix 2](#)
- Collect clean-catch, mid-stream urine sample for urinalysis in all subjects and for UPT for women of child bearing potential
- Assess adverse events and record concomitant medications: If subjects have an ongoing serious adverse event, the subject should be followed until the adverse event is resolved or returns to baseline. All possible attempts should be made to document resolution of acute and chronic toxicities.

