A treatment by study center interaction effect will be added to the MMRM ANCOVA (or ANOVA) model used for the analyses of the primary efficacy variable. If a statistically significant treatment by study center interaction effect is noted using a 0.1 level of significance, then separate analyses will be performed for each study center.

In addition to the week 12 comparisons, the change from baseline to week 2 and week 6 will also be analyzed from the same MMRM ANCOVA model using 95% CIs for the between-group mean changes. The secondary efficacy endpoint, changes in HbA1c over time will be assessed descriptively using graphical methods

To examine the dose response, tests for linear and quadratic dose-response relationships between the doses (0 [placebo], 5, 10 and 20 mg bexagliflozin) and the change from baseline in HbA1c at week 12 will be conducted using a general linear model and appropriate orthogonal polynomial contrasts.

Fasting plasma glucose, systolic and diastolic blood pressure, and weight will be analyzed using the same MMRM ANCOVA model used in the primary efficacy analysis.

For each subject, the post-baseline HbA1c values on or before week 12 will be assigned to a category of $< 7\%$ or $\geq 7\%$. Incidences of reduction of HbA1c to $< 7\%$ will be analyzed using a logistic regression model with effects for treatment, study center and baseline HbA1c. Odds ratio and the corresponding 95% CI will also be presented.

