1 INTRODUCTION

Study THR-1442-C-449 is a Phase 2b, multi-center, double-blind, placebo-controlled, dose range finding study. The goals of the study are to evaluate the efficacy and safety of once daily bexagliflozin at 5 mg, 10 mg and 20 mg strengths compared to placebo in either treatment-naïve type 2 diabetic subjects or subjects previously treated with one oral hypoglycemic agent (OHA) and to identify the optimal dose(s) for further clinical study.

The statistical analysis plan (SAP) contains a detailed description of the data presentations and statistical analyses that will be included in the clinical study report (CSR) for Protocol THR-1442-C-449. The statistical methods and analyses described here are based on those presented in Section 9 of the study protocol (Version 2: 16 February 2015).

Blood samples for a population pharmacokinetic (PK) analysis will be collected and the required plasma concentration determined, however, the PK parameters will be assessed separately as a population PK analysis (i.e., the population PK analysis will not be described in this SAP).

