2.2.3 Efficacy Assessments

Efficacy assessments will include blood draws for a glycemic control laboratory panel, including HbA1c and FPG, body weight, and systolic and diastolic blood pressure (BP).

Blood samples for HbA1c and FPG will be obtained at Screening (Visit S1), Run-in (Visit S5), Treatment Period Visits 2, 3, 4 and Follow-up Visit 5. Body weight will be measured at Screening (Visit S1), Washout (Visit S2), Run-in (Visit S5), Treatment Period Visits 2, 3, 4 and Follow-up Visit 5. Supine, sitting and standing

BP measurements will be obtained at Screening (Visit S1), Run-in (Visits S4 and S5), Treatment Period Visits 2, 3, 4 and Follow-up Visit 5.

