3.3.2 Secondary Efficacy Variables

- Change in HbA1c from baseline over time
- Change in FPG from baseline over time
- Percentage of subjects with HbA1c <7% post-baseline
- Change in systolic and diastolic blood pressure from baseline over time
- Change in body weight from baseline over time

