14.2.2.3	Least Squares Summary Mixed Model Repeated-Measure (MMRM) Analysis of Fasting Plasma Glucose (mmol/L): Change from Baseline	Full Analysis Set
14.2.3.1	Summary of Sitting Systolic Blood Pressure (mmHg) by Visit: Observed and Change from Baseline	Full Analysis Set
14.2.3.2	Mixed Model Repeated-Measure (MMRM) Analysis of Sitting Systolic Blood Pressure (mmHg): Change from Baseline	Full Analysis Set

Table Number	Table Title	Analysis Set
14.2.3.3	Least Squares Summary Mixed Model Repeated-Measure (MMRM) Analysis of Sitting Systolic Blood Pressure (mmHg): Change from Baseline	Full Analysis Set
14.2.4.1	Summary of Sitting Diastolic Blood Pressure (mmHg) by Visit: Observed and Change from Baseline	Full Analysis Set
14.2.4.2	Mixed Model Repeated-Measure (MMRM) Analysis of Sitting Diastolic Blood Pressure (mmHg): Change from Baseline	Full Analysis Set
14.2.4.3	Least Squares Summary Mixed Model Repeated-Measure (MMRM) Analysis of Sitting Diastolic Blood Pressure (mmHg): Change from Baseline	Full Analysis Set
14.2.5.1	Summary of Body Weight (kg) by Visit: Observed and Change from Baseline	Full Analysis Set
14.2.5.2	Mixed Model Repeated-Measure (MMRM) Analysis of Body Weight (kg): Change from Baseline	Full Analysis Set
14.2.5.3	Least Squares Summary Mixed Model Repeated-Measure (MMRM) Analysis of Weight (kg): Change from Baseline	Full Analysis Set
14.2.6	Logistic Regression Analysis of Subject Achieving Post-baseline HbA1c <7%, Excluding HbA1c Data Obtained After Rescue Medication	Full Analysis Set
Safety Endpoints – Adverse Events		
14.3.1.1	Overall Summary of Treatment Emergent Adverse Events	Safety Analysis Set
14.3.1.2	Summary of Treatment Emergent Adverse Events by MedDRA System Organ Class and Preferred Term	Safety Analysis Set
14.3.1.3	Summary of Treatment Emergent Adverse Events by MedDRA System Organ Class, Preferred Term and Maximum Severity	Safety Analysis Set

Table Number	Table Title	Analysis Set
14.3.1.4	Summary of Related Treatment Emergent Adverse Events by MedDRA System Organ Class and Preferred Term	Safety Analysis Set
14.3.2	Summary of Treatment Emergent Adverse Events of Special Interest by MedDRA System Organ Class and Preferred Term	Safety Analysis Set
14.3.3	Summary of Hypoglycemic Events by Category and Logistic Regression Analysis of Subjects with a Post-baseline Hypoglycemic Event	Safety Analysis Set
Safety Endpoints – Clinical Laboratory		

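### The SAP drops the protocol's Week 12 limit from the HbA1c <7% endpoint, so a completer can count as a responder on the Week 14 follow-up sample alone

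*SAP*

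**What the plan says.** Protocol 9.5 sets the rule for this secondary endpoint: for each subject, "the post-baseline HbA1c values on or before week 12 will be assigned to a category of" below 7% or at least 7%, followed by a logistic regression.

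SAP 3.8.2 gives the corresponding rule without a time limit: "For each subject, post-baseline HbA1c values will be reviewed and subjects with at least one post-baseline HbA1c value" below 7% are flagged as responders. The same paragraph excludes values after the start of rescue medication and nothing else. The variable list in SAP 3.3.2 reads "Percentage of subjects with HbA1c <7% post-baseline", and Table 14.2.6 is titled "Logistic Regression Analysis of Subject Achieving Post-baseline HbA1c <7%, Excluding HbA1c Data Obtained After Rescue Medication". Neither restores the limit.

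SAP 1 states: "The statistical methods and analyses described here are based on those presented in Section 9 of the study protocol". SAP 3.8.2 does not present its rule as a change from the protocol.

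On sampling, SAP 2.2.3 gives this schedule: "HbA1c and FPG will be obtained at Screening (Visit S1), Run-in (Visit S5), Treatment Period Visits 2, 3, 4 and Follow-up Visit 5". On timing, Protocol 3.4 says: "Subjects will receive 12 weeks of treatment and be followed for 2 weeks after the last dose". Protocol 7.4.1 places V5 at "week 14 or two weeks after the last dose of investigational product if a subject early terminates". SAP Table 2 (section 3.1.9) lists Week 14 among the post-baseline assessments, with a window of Days 93 to 105.

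**The concern.** The two documents can classify the same completer differently. The sample that makes the difference is taken after treatment has ended, and it gives each completer one more chance to fall below the threshold. Reported response percentages, odds ratios, confidence intervals and p-values for a listed secondary objective would then depend on which document the programmer followed.

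The point concerns only the completer whose sole value below 7% is the Week 14 value. Early-termination V5 samples taken by Week 12 count under Protocol 9.5 and are not in question. Nor is the SAP's choice to let a single value below 7% suffice.

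**Working it through.** **1. The texts side by side, for a completer without rescue**

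| Scheduled HbA1c sample | Protocol 9.5 | SAP 3.8.2 as written |
|---|---|---|
| Week 2 (V2) | counts | counts |
| Week 6 (V3) | counts | counts |
| Week 12 (V4) | counts | counts |
| Week 14 (V5) | does not count | counts |

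Three scheduled samples can make a responder under the protocol and four under the SAP.

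**2. Does another rule remove the Week 14 value?** The rescue exclusion does not do so by design: Protocol 3.2.2 sends completers to their own physician for further diabetes treatment only after the exit visit. Elsewhere the SAP states a time limit where it wants one. The primary variable in 3.3.1 runs to Week 12, and hypoglycemia in 3.9.1.7 is limited to the double-blind period. SAP 3.8.2 has no equivalent wording.

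**3. Visit days.** Targets are Day 85 for V4 and Day 99 for V5, each with a window of 3 days either side (Protocol 7, SAP 3.1.9).
- V4 on schedule: 85 ± 3 = Days 82 to 88, inside the Week 12 window (78 to 92).
- V5 on schedule: 99 ± 3 = Days 96 to 102, inside the Week 14 window (93 to 105).
- A cut-off at Day 92 keeps every on-schedule V4 and removes every on-schedule V5. A literal Day 85 cut-off would also lose V4 samples taken on Days 86 to 88.

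**4. The plan's own figure.** No figure is stated for this endpoint. The nearest is the primary-endpoint power in Protocol 9.2: difference 0.5, SD 0.9, 70 per arm, two-sided 5%. The noncentrality is (0.5/0.9) × √(70/2) = 3.29 on 138 degrees of freedom, giving 90.4% power against the stated 90% or so. It reproduces, and it does not depend on the present point.

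**5. Illustrative size, first simulation** (72 scenarios, 200,000 subjects per arm each).
- From the documents: SD of change at Week 12 of 0.9, 20 mg effect of -0.5, baseline restricted to 7.0 to 8.5%, 80 per arm.
- Assumed and varied: trajectory type (random walk, constant SD, subject-specific slope); within-subject SD 0.10 or 0.20; latent baseline mean 7.7 (SD 0.5) or 7.9 (SD 0.6); 70, 85 or 100% of the effect remaining at Week 14; placebo change at Week 12 of 0 or +0.2.
- Assumed and fixed: 30/70/100% of the effect at Weeks 2/6/12, placebo mean at Week 14 equal to Week 12, values rounded to 0.1, no dropout or rescue.

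The contrast is any value below 7% to Week 12 against any value to Week 14.

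| Quantity | To Week 12 | Change from adding Week 14 |
|---|---|---|
| Placebo response | 14 to 32% | +1.4 to +4.5 points (1.2 to 3.6 of 80) |
| 20 mg response | 29 to 48% | +0.7 to +5.2 points (0.6 to 4.1 of 80) |
| Baseline-adjusted odds ratio, 20 mg to placebo | 1.9 to 2.8 | -0.58 to +0.11 |
| Log odds ratio | standard error 0.35 to 0.43 at 80 per arm | -0.23 to +0.05, at most 0.55 standard errors |

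By trajectory, the odds ratio changes by -0.08 to +0.11 (constant SD), -0.30 to -0.03 (random walk) and -0.58 to -0.21 (subject slope).

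**6. Second simulation, different assumptions** (400,000 subjects). Baseline is uniform on 7.0 to 8.5. SD of change at Week 12 is 0.9 or 0.5. Mean change is 0 on placebo and -0.15/-0.35/-0.5 at Weeks 2/6/12 on 20 mg. The Week 12 to Week 14 correlation is varied. Results for SD 0.9, with gains computed before rounding:

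| Correlation, Weeks 12 and 14 | Placebo | 20 mg, Week 14 mean -0.5 | 20 mg, Week 14 mean -0.4 |
|---|---|---|---|
| 0.70 | 28.9 to 35.2% (+6.3) | 46.1 to 54.3% (+8.2) | 46.2 to 52.9% (+6.7) |
| 0.90 | 29.0 to 32.4% (+3.4) | 46.0 to 50.5% (+4.4) | 46.2 to 49.2% (+3.1) |
| 0.97 | 29.0 to 30.7% (+1.8) | 46.2 to 48.5% (+2.3) | 46.2 to 47.4% (+1.2) |

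Including SD 0.5, the gains are 1.1 to 6.3 points on placebo and 0.5 to 8.2 points on 20 mg.

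The crude odds ratio at correlation 0.90 shows why the direction is not fixed:
- Week 14 mean -0.4: (0.462/0.538)/(0.290/0.710) = 2.10 becomes (0.492/0.508)/(0.324/0.676) = 2.02, a fall of 0.08.
- Week 14 mean -0.5: (0.460/0.540)/(0.290/0.710) = 2.09 becomes (0.505/0.495)/(0.324/0.676) = 2.13, a rise of 0.04.

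**The case against.** The best defence is that the SAP is silent rather than contradictory. No sentence says that Week 14 HbA1c counts. SAP 1 ties the methods to protocol Section 9, and SAP 3.8.1 frames HbA1c efficacy around Weeks 2, 6 and 12. The protocol's own objectives, endpoint list and synopsis carry no time limit; only 9.5 does. This does not close the gap. SAP 1 is a general statement, SAP 3.8.1 describes the primary model, and 9.5 is the protocol's operative rule. Read literally, SAP 3.8.2 admits the V5 value.

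A second argument is that HbA1c reflects two to three months of glycemia (Protocol 3.3 and 6.13), so a sample two weeks off drug still mostly reflects treatment. That is fair and limits the practical harm. It does not make the two responder counts agree.

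Third, the absence of a marked change is weak evidence of a mistake, because the same SAP paragraph adds a rescue exclusion and a prior-treatment covariate that 9.5 does not state for this endpoint. That stands: the omission could be deliberate. If so, it needs to be stated.

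Fourth, the magnitude is assumption-driven, and the two simulations give different ranges. Both also apply an any-value rule up to Week 12, which 9.5 does not spell out. This stands too. The figures isolate the effect of adding Week 14 and show only its order of magnitude.

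**Conclusion.** The concern holds. Protocol 9.5 limits the HbA1c <7% endpoint to values up to Week 12, SAP 3.8.2 does not, and a scheduled off-drug sample exists that the omission lets in. The conflict rests on the text alone.

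Its size cannot be derived from the documents. Across both sets of assumptions the extra sample adds between 0.5 and 8.2 percentage points of responders per arm. The odds ratio may move either way, by about half a standard error at most in the first simulation. The endpoint is secondary and exploratory, without multiplicity control (Protocol 9.1.2, SAP 3.1.4), and no conclusion on the primary endpoint, dose response or sample size is affected. It should be corrected because the conflict is clear and the correction is cheap, not because a large bias is expected.

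**What to change.** Before unblinding:

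- In SAP 3.8.2, restrict the classification to post-baseline values up to Week 12 and state that Week 14 follow-up values do not count for this endpoint. Carry the same limit into SAP 3.3.2 and the title of Table 14.2.6 so that all three agree.
- Say whether Week 12 ends on Day 85 or at the end of the SAP Table 2 window, Day 92. Day 92 fits the permitted visit windows.
- Leave early-termination V5 samples taken by Week 12 in the analysis, as Protocol 9.5 has them.

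If the sponsor did intend Week 14 to count, the SAP should instead record this as a departure from Protocol 9.5, with the reason.

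The cost is wording in two SAP sections and one table title, with no new data or analysis. Reported response may be a few percentage points lower in each arm than under the SAP as written.

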2.2 Secondary Objectives

The secondary objectives of this study are the following:

- To assess the change in HbA1c over time
- To assess the efficacy of bexagliflozin tablets in lowering fasting plasma glucose (FPG) over time
- To assess the efficacy of bexagliflozin based on the proportion of subjects who reach the American Diabetes Association (ADA) and the Japan Diabetes Society target HbA1c of <7%
- To assess the effect of bexagliflozin on systolic and diastolic blood pressure over time
- To assess the effect of bexagliflozin on body weight over time
- To assess the safety of bexagliflozin in subjects with T2DM

Other exploratory objective includes:

- Population pharmacokinetic evaluation of bexagliflozin plasma concentration

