4.2 Inclusion Criteria

Prospective subjects must be:

1. Men or women ≥ 20 years of age at screening. Women of childbearing potential must test negative by urine pregnancy test and agree to abstain from coitus or use contraception during the entire study period to avoid any possible pregnancy. Females who are surgically sterile (by reason of hysterectomy or oophorectomy) or postmenopausal (most recent menses more than 12 months prior to screening) are eligible if they test negative by urine pregnancy test.
2. Treatment naïve (*i.e.*, have never received prescription anti-diabetic medications or have received no more than 14 days of prescription medications for diabetes in the 12 weeks prior to enrollment) or currently taking one OHA in combination with diet and exercise
3. Diagnosed with T2DM with HbA1c levels at screening between 7.0% and 8.5% (inclusive) if treatment naïve or with HbA1c levels between 6.5 and 8.5% (inclusive) if on one oral anti-diabetic medication
4. Currently having a body mass index (BMI) ≤ 40 kg/m²
5. Taking stable doses of medication for hypertension or hyperlipidemia as determined by adherence to a regimen that has not changed for at least 30 days prior to screening (if applicable)
6. Able to comprehend the study participation requirements and willing to provide written informed consent in accordance with institutional and regulatory guidelines
7. Able to maintain adequate glycemic control at the run-in visit (for subjects who complete the washout)
8. Having an HbA1c between 7.0 and 8.5% (inclusive) prior to randomization (day -3 to -5)
9. Capable of adhering to the investigational product administration requirements as evidenced by omission of no more than one dose of run-in medication

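### The HbA1c <7% endpoint reports subjects who were ever below 7%, and no planned output gives the proportion below 7% at Week 12

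*SAP*

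**What the plan says.** Protocol 2.2 sets as a secondary objective "the proportion of subjects who reach the American Diabetes Association (ADA) and the Japan Diabetes Society target HbA1c of <7"%. SAP 3.3.2 turns this into the variable "Percentage of subjects with HbA1c <7% post-baseline", with no time point.

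SAP 3.8.2 gives the derivation. It begins "For each subject, post-baseline HbA1c values will be reviewed and subjects with at least one post-baseline HbA1c value" below 7% and flags those subjects. It then states "HbA1c values obtained after start of rescue medication will be excluded from this analysis". The flag is tabulated ("The number and percentage of subjects with at least one HbA1c value $<7\%$ will be summarized by treatment group") and is the dependent variable of a logistic model with treatment, center, baseline HbA1c and prior treatment status. Table 14.2.6 is the only planned output for this endpoint, and SAP 3.8.2 rules out sensitivity analyses on secondary endpoints.

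Protocol 9.5 is slightly different: "For each subject, the post-baseline HbA1c values on or before week 12 will be assigned to a category of" below 7% or not. It stops at Week 12 but does not say which visit decides. The SAP does not carry that limit over, although "HbA1c and FPG will be obtained at Screening (Visit S1), Run-in (Visit S5), Treatment Period Visits 2, 3, 4 and Follow-up Visit 5", and Visit 5 (Week 14) is two weeks after the last dose.

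Randomization requires "Having an HbA1c between 7.0 and 8.5% (inclusive) prior to randomization (day -3 to -5").

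**The concern.** A percentage of subjects reaching the <7% target in a 12-week trial will usually be read as the percentage at target at the end of treatment. The SAP reports something else: the percentage with at least one value below 7%. The two differ for any subject who dips and returns. The rescue sentence does not close the gap. It removes values after rescue, but a value below 7% before rescue still sets the flag.

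The gap matters more here because the lowest permitted entry value is also the response threshold. A subject entering at 7.0% needs a fall of only 0.1 point at one visit, and there are at least three visits at which it can happen. Protocol 3.3 notes that HbA1c reflects 2 to 3 months of glycemia, so a Week 2 value says little about 12 weeks of treatment.

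At stake are the percentages in Table 14.2.6 and their match to the primary variable, which SAP 3.3.1 fixes at Week 12.

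**Working it through.** **The plan's own figure.** The documents give no expected rate for this endpoint. The effect and SD used below come from Protocol 9.2, and they reproduce its power statement: n per arm = 2 × (1.960 + 1.282)² × 0.9² / 0.5² = 68.1, so 69. With 70 per arm the noncentral t gives 90.4%, against the stated figure of about 90%.

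**Direction.** The set below 7% at Week 12 is contained in the set below 7% at any of Weeks 2, 6 and 12. In each arm the any-visit percentage therefore cannot be lower than the Week 12 percentage for the same subjects.

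**Size: main simulation.**
- From the documents: baseline range 7.0 to 8.5%; active Week 12 effect -0.5%; Week 12 change SD 0.9% as the top value.
- Assumed: baseline 7 + 1.5 × Beta(1.5, 1.8); placebo mean change 0; 25%, 65% and 100% of the effect at Weeks 2, 6 and 12; change SD at those visits 0.35, 0.6 and 1.0 times the Week 12 SD; adjacent-visit correlation 0.5 or 0.7, with its square between Weeks 2 and 12; no dropout, rescue or Week 14 value.

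Returned means at or above 7% at Week 12, as a share of any-visit responders. It equals (ever − Week 12) / ever.

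| Week 12 SD | Corr. | Placebo: Week 12 / ever | Returned | Active: Week 12 / ever | Returned | Odds ratio: Week 12 / ever |
|---|---|---|---|---|---|---|
| 0.5 | 0.5 | 13.6 / 17.5% | 22% | 38.8 / 44.1% | 12% | 4.0 / 3.7 |
| 0.5 | 0.7 | 13.6 / 16.1% | 16% | 38.8 / 42.1% | 8% | 4.0 / 3.8 |
| 0.7 | 0.5 | 19.4 / 25.3% | 23% | 41.0 / 48.7% | 16% | 2.9 / 2.8 |
| 0.7 | 0.7 | 19.4 / 23.3% | 17% | 41.0 / 45.9% | 11% | 2.9 / 2.8 |
| 0.9 | 0.5 | 24.2 / 32.1% | 25% | 42.6 / 52.4% | 19% | 2.3 / 2.3 |
| 0.9 | 0.7 | 24.2 / 29.5% | 18% | 42.6 / 48.9% | 13% | 2.3 / 2.3 |

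The excess is 2.5 to 8 points on placebo and 3 to 10 on active. With 80 per arm that is 0.025 × 80 = 2 to 0.08 × 80 = 6 placebo subjects. The difference between arms in percentage at target grows by about 1 to 2 points.

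**Sensitivity to the assumptions.** A second simulation used a uniform or truncated-normal baseline, values rounded to 0.1, and correlations of 0.5 to 0.9. The change SD either grew over time (0.3, 0.6, 0.9) or was flat at 0.5 or 0.9. Over Weeks 2, 6 and 12, 8 to 48% of placebo responders and 5 to 29% of active responders were at or above 7% at Week 12. With a growing SD the crude odds ratio stayed put (about 2.3 to 2.4 at Week 12, 2.2 to 2.4 ever). With a flat SD it moved towards 1 (from 2.3–4.3 to 1.8–3.2). Letting Week 14 count raised the returned shares to 20 to 55% and 10 to 36%.

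**The entry floor.** With no true change and a within-subject SD of 0.1 to 0.3, a subject with a measured baseline of exactly 7.0% is flagged 61 to 69% of the time over three visits, and 37 to 43% of the time at Week 12 alone.

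**The case against.** The rule is stated openly and fits the objective's wording. Reaching a target can mean reaching it at any time, Protocol 9.5 refers to values in the plural, and no section calls this the proportion controlled at Week 12. That stands: the SAP does not contradict its objective. The point is that the Week 12 proportion is nowhere planned.

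The endpoint is exploratory (Protocol 9.1.2), and an excess of 2.5 to 8 points is of the order of the standard error of one arm's percentage: √(0.2 × 0.8 / 80) = 4.5 points. That also stands and limits the weight of the point.

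A reader might infer several stronger things that the documents do not support:
- *The rule favors bexagliflozin.* Both arms rise. The odds ratio is nearly unchanged or moves towards 1, and the between-arm difference grows by only 1 to 2 points in the main settings.
- *Dose choice is compromised.* That rests on HbA1c change against placebo, with Week 12 contrasts and a Week 12 dose-response test (SAP 3.8.1).
- *A Week 12 rule removes chance crossing of the 7% line.* It does not. Placebo still shows 14 to 24% below 7% at Week 12 with no mean change. The entry floor causes most of this, and baseline HbA1c is already a covariate.
- *Many rescued subjects are counted as successes, or unequal visit numbers distort the result.* Both are possible under the text but unquantified. The schedule is the same for everyone, and the simulations contain no rescue or dropout.

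**Conclusion.** The point holds as one about what is reported. SAP 3.8.2 estimates the proportion ever below 7%, keeps as responders subjects who have returned to 7% or above by Week 12 or are later rescued, and leaves the Week 12 proportion without any planned summary or model.

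In the main settings, 16 to 25% of placebo responders and 8 to 19% of active responders are not below 7% at Week 12. The direction is certain. The size rests on assumed baseline spread, visit correlations and time course, and would be larger if early HbA1c changes vary as much as those at Week 12. That the odds ratio is nearly unchanged also depends on variability growing over time. The primary analysis, sample size and dose-response test are untouched. The change is worth making because it is specific and cheap, not because the trial's conclusions depend on it.

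**What to change.** - In SAP 3.3.2, SAP 3.8.2 and Table 14.2.6, make HbA1c <7% at the Week 12 analysis visit, using pre-rescue values only, the main classification. Keep the logistic model as it is.
- Keep the at-least-one-value count as a supportive row labelled as ever below 7%, Weeks 2–12. The label also restores the Week 12 limit in Protocol 9.5, so that an off-treatment Week 14 value cannot count.
- Use observed Week 12 data for the main row. Protocol 9.1.1 and SAP 3.1.7 say that missing data are not imputed for endpoints other than the primary.
- Beside it, show a version that counts rescued subjects and those with no Week 12 value as not at target. This is a form of imputation. If it is to be the main version, amend Protocol 9.1.1 and SAP 3.1.7. In either case, amend the SAP 3.8.2 sentence that rules out sensitivity analyses on secondary endpoints, so that both versions can stand.

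Cost: SAP wording, a derived variable for each version and the added table rows, with no new data. A protocol amendment is needed only if the rescued-or-missing version becomes the main one. The downside is a percentage at target a few points lower in every arm. The observed-data row will also have a smaller denominator, and its effect is not estimated here.
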